7.1 Discontinuation of study treatment

Patients may voluntarily discontinue study treatment for any reason at any time.

The investigator **must** discontinue study treatment for a given patient if, on balance, he/she believes that continuation would be detrimental to the patient's well-being.

Study treatment **must** be discontinued under the following circumstances:

- Patient withdraws consent
- Pregnancy
- Grade 3 or higher allergic reaction
- Acute, Grade 3 or higher infection as judged by the Investigator

The study treatment should be discontinued if:

- Clinically significant worsening of Graves' disease, eg. beta-blocker unable to control the symptoms of hyperthyroidism, at the discretion of the Investigator.
- New onset atrial fibrillation or angina.
- On balance, the investigator believes that continuation would be detrimental to the patient's well-being.

Discontinuation of study treatment will be at the discretion of the Investigator, under the following circumstances:

- Use of prohibited treatment as per [Section 5.2](#).
- Any other protocol deviation that results in a significant risk to the patient's safety

Patients who discontinue study treatment or who decide they do not wish to participate in the study further should NOT be considered withdrawn from the study UNLESS they withdraw their consent (see [Section 7.3](#)). Where possible, they should return for the assessments defined in the [Assessment table](#). If they fail to return for these assessments for unknown reasons, every effort (e.g. telephone, e-mail, letter) should be made to contact them as specified in [Section 7.2.1](#). Patients who discontinue the drug before having completed 4 weeks of treatment and 4 week efficacy and safety evaluations will be replaced with a newly enrolled patient.

7.2 Study completion and post-study treatment

Each enrolled patient will be required to complete the study in its entirety and thereafter no further study treatment will be made available to them. Study completion is defined as when the last patient completes their End of Study visit, and any repeat assessments associated with this visit have been documented and followed-up appropriately by the Investigator, or in the event of an early study termination decision, the date of that decision.

After the study participation, the patients will continue to be treated by his/her general practitioner according to the local standard clinical management related to the underlying disease.

The investigator must provide follow-up medical care for all patients who are prematurely withdrawn from the study, or must refer them to appropriate ongoing care.

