3.3 Rationale of dose/regimen, duration of treatment

Dosing rationale

The dosing rationale for this study is determined based on the safety, preliminary PK/PD data from the FIH study, and preclinical pharmacology data. It is further supported by adequate safety multiples from preclinical toxicological studies, relevant PD effects in tissues in non-human primates, and recently disclosed data from ASKP1240 in kidney transplantation.

The dosing regimen of 10 mg/kg Q4W with an additional dose at Day 15 is predicted to maintain the trough plasma concentration of CFZ533 above 50 µg/mL, which is thought to be needed to ensure complete CD40 pathway blockade in target tissues (Figure 3-2). In the thyroid glands of patients with Graves' disease, CD40 expression is increased (Smith et al 1999, Hwang 2009, Mysliwiec et al 2007a, Mysliwiec et al 2007b). The additional dose on Day 15 is needed to overcome efficient target mediated disposition and loss of target saturation in tissues where CD40 expression is increased.

Corporate Confidential Information

In [Goldwater et al 2013](#) ASKP1240 demonstrated similar PK properties as compared to CFZ533. Modeling of disclosed PK data from ASKP1240 in Transplantation ([Harland et al 2015](#)) characterized the biology (expression and turnover) of CD40 in conditions where CD40 expression is increased. From a quantitative point of view, the biology of CD40 in GD is not fully characterized, but literature data have confirmed an increase of CD40 expression in these patients. The transplant situation is thought to represent these conditions.

Corporate Confidential Information

Corporate Confidential Information

Data for another monoclonal antibody that blocks CD40, ASKP1240 - A recent analysis of the disclosed PK/efficacy data from ASKP1240 (Astellas' anti-CD40 antibody) in solid organ transplantation ([Harland et al 2015](#)) indicated that efficient target mediated antibody clearance in tissue could result in loss of CD40 blockade and likely loss of efficacy, as a consequence of a significant increase of CD40 expression in target tissues.

Duration of Treatment

No previous experience with an anti-CD40 blocking agent exists in patients with GD. CFZ533 at 10 mg/kg IV is associated with up to 10 week full receptor occupancy (RO) in patients with RA. Therefore, 12-week treatment with CFZ533 at 10 mg/kg Q4W with an additional dose on Day 15 is anticipated to result in full CD40 RO up to approximately 5 months.

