7.5 Early study termination

The study can be terminated at any time for any reason by Novartis. Should this be necessary, patients should be seen as soon as possible and treated as a prematurely withdrawn patient. The investigator may be informed of additional procedures to be followed in order to ensure that adequate consideration is given to the protection of the patient's interests. The investigator will be responsible for informing IRBs/IECs of the early termination of the trial.

8 Procedures and assessments

Table 8-1 Assessment schedule

Patients should be seen for all visits on the designated day, with the assessments performed as per schedule, within the allowed “visit/assessment window” specified in the Site Operations Manual.

Study Phase	Screening	Baseline	Treatment								Follow-up				EOS visit		
			V101		V102		V103		V104		V199		V201	V202	V203	V204	
Visit Numbers ¹	V1	V99 ¹²														V299	
Study Day(s)	Up to -28	-1	1		15		29		57		85		113	141	169	211	253
Time (post-dose)	-	-	0h ⁹	1h ⁹	-	-	-	-	-								
Informed consent	X																
Inclusion / Exclusion criteria	X	X ²															
Medical history/current medical conditions	X																
Demography	X																
Hepatitis and HIV Screen	X																
TB Test ¹⁰	X																
EBV Screen	X																
Alcohol Test and Drug Screen	X																
Blood Pressure and Pulse Rate	X	X	X	X	X	X	X	X	X	X	X	X	X	X	X	X	X
Physical examination	X		X		X		X			X		X			X	X	X
Body temperature	X	X	X		X		X		X		X		X	X	X	X	X
Body height	X																
Body weight	X	X ¹³					X		X		X		X		X		X
ECG evaluation	X	X	X		X		X		X		X		X	X	X	X	X
Pregnancy test	X	X ¹³			X		X		X		X		X		X		X
Dose administration			X		X		X		X		X						
Blood chemistry ⁴	X	X	X				X				X		X		X		X

Study Phase	Screening	Baseline	Treatment								Follow-up				EOS visit		
Visit Numbers ¹	V1	V99 ¹²	V101		V102		V103		V104		V199		V201	V202	V203	V204	V299
Study Day(s)	Up to -28	-1	1		15		29		57		85		113	141	169	211	253
Time (post-dose)	-	-	0h ⁹	1h ⁹	-	-	-	-	-								
Corporate Confidential	X	X	X				X				X		X		X		X
Hematology	X	X	X		X		X		X		X		X		X		X
Urinalysis	X	X	X				X				X		X		X		X
Cytokine assessment			X	X	X	X	X	X	X	X	X	X					
Coagulation Panel		X ¹³		X		X		X		X		X	X	X		X	X
Concomitant therapies													as required				
Serious adverse events													as required				
Adverse events													as required				
Immunogenicity ³			X						X				X	X	X		X
Comments													as required				

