9.2.2 SAE reporting

To ensure patient safety, every SAE, regardless of causality, occurring after the patient has provided informed consent and until the study completion, must be reported to Novartis within 24 hours of learning of its occurrence as described below. Any SAEs experienced after the completion of the study should only be reported to Novartis if the investigator suspects a causal relationship to study treatment.

Recurrent episodes, complications, or progression of the initial SAE must be reported as follow-up to the original episode, regardless of when the event occurs. This report must be submitted within 24 hours of the investigator receiving the follow-up information. An SAE that is considered completely unrelated to a previously reported one should be reported separately as a new event.

SAEs (initial and follow-up) that are recorded electronically in the Electronic Data Capture system should be entered, saved and e-signed within 24 hours of awareness of the SAE or changes to an existing SAE. These data will automatically be submitted to Novartis Drug Safety & Epidemiology immediately after investigator signature or 24 hours after entry, whichever occurs first. Study site personnel must also inform the Clinical Trial Leader.

Follow-up information provided should describe whether the event has resolved or continues, if and how it was treated, whether the treatment code was broken or not and whether the patient continued or withdrew from study participation. Each re-occurrence, complication, or progression of the original event should be reported as a follow-up to that event regardless of when it occurs.

If the SAE is not previously documented in the Investigator's Brochure and is thought to be related to the investigational treatment, a Drug Safety and Epidemiology Department associate may urgently require further information from the investigator for Health Authority reporting. Novartis may need to issue an Investigator Notification (IN) to inform all investigators involved in any study with the same investigational treatment that this SAE has been reported. Suspected Unexpected Serious Adverse Reactions (SUSARs) will be collected and reported to the competent authorities and relevant ethics committees in accordance with EU Guidance 2011/C 172/01 or as per national regulatory requirements in participating countries.

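### On early termination, all-cause reporting of new SAEs ends on the decision date, even for patients just dosed and before their closing visit

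*Protocol*

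**What the plan says.** Protocol 7.2 contains the only formal definition of study completion. It is set for the study as a whole: "Study completion is defined as when the last patient completes their End of Study visit", with any associated repeat assessments documented and followed up, "or in the event of an early study termination decision, the date of that decision".

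Protocol 9.2.2 ties SAE reporting to that term. The all-cause obligation covers "every SAE, regardless of causality, occurring after the patient has provided informed consent and until the study completion". The rule then narrows: "Any SAEs experienced after the completion of the study should only be reported to Novartis if the investigator suspects a causal relationship to study treatment". Recurrences, complications and progression of an SAE already reported are exempt from the cut-off; they "must be reported as follow-up to the original episode, regardless of when the event occurs".

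On early termination, Protocol 7.5 says that "patients should be seen as soon as possible and treated as a prematurely withdrawn patient". It allows additional protective procedures to be communicated to the investigator, but names none and sets no SAE reporting period.

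The planned course is longer. Protocol 3.1 has dosing on Days 1, 15, 29, 57 and 85, then 24 weeks of follow-up to a study completion evaluation on Day 253. Protocol 2.2 sets a safety objective of up to 36 weeks. Protocol 3.3 states that "CFZ533 at 10 mg/kg IV is associated with up to 10 week full receptor occupancy (RO) in patients with RA".

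The visible text of the SAP does not address the SAE reporting window.

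**The concern.** The two definitions look harmless apart. Combined, they make the reporting window depend on an administrative date and not on when a patient was last exposed. Protocol 7.4 lists safety findings that can lead to termination, among them drug-related SAEs in two patients, one cytokine release syndrome, and one treatment-related thromboembolic event of Grade 3 or higher. Any of these could arise while other patients are mid-treatment.

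From the decision date, whether a new SAE in a dosed patient reaches the sponsor depends on one investigator's causality judgement. The study has one open-label arm and neither a data monitoring committee nor an adjudication committee (Protocol 10.3, 10.4), and Protocol 3.6.1 says the drug has never been used in Graves' disease. An unrecognised risk may first show up as events that look unrelated one at a time, and all-cause reporting exists to catch that. Protocol 3.6.2 expects general immunosuppression at full receptor occupancy, so the cut-off can fall in a period when the drug is still fully active.

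There is also an asymmetry. Under Protocol 7.1, a patient who stops treatment individually is not regarded as withdrawn without withdrawal of consent and is asked to keep attending scheduled assessments; all-cause reporting continues for that patient. A patient whose dosing ends because the whole study was stopped gets a shorter window.

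**Working it through.** **Step 1: the plan's own time figures.** Inputs: last dose on Day 85 and final evaluation on Day 253 (Protocol 3.1); receptor occupancy figures (Protocol 3.3).
- Follow-up after the last dose: 253 − 85 = 168 days; 168 / 7 = 24 weeks. This reproduces the stated 24 weeks.
- Day 1 to Day 253: 253 − 1 = 252 days; 252 / 7 = 36 weeks. This matches the horizon of the safety objective.
- Full occupancy under the regimen: 12 weeks of treatment + 10 weeks = 22 weeks; 22 × 7 / 30.44 ≈ 5.1 months. This matches the stated 5 months or so.

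**Step 2: apply 7.2 and 9.2.2 to a termination decision on day D of a patient's schedule.**
- 7.2: study completion = decision date.
- 9.2.2: all-cause reporting of new SAEs runs to study completion, hence to the decision date.
- All-cause days remaining after the decision: 0, whatever the date of the last dose.
- 7.5: the closing visit follows the decision. A new SAE that starts between the decision and that visit, and is judged unrelated, need not be reported under 9.2.2.

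**Step 3: size of the gap.** For a patient dosed on the decision day, the lost window measured to that patient's own planned Day 253 is 253 − D:

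| Decision and dose on Day | Days lost | Weeks lost |
|---|---|---|
| 1 | 252 | 36 |
| 15 | 238 | 34 |
| 29 | 224 | 32 |
| 57 | 196 | 28 |
| 85 | 168 | 24 |

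Of this, up to 10 × 7 = 70 days could be spent at full receptor occupancy, if the rheumatoid arthritis figure carries over to Graves' disease.

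**Step 4: what stays reportable after the decision date.**
- New SAEs suspected to be related: yes (9.2.2).
- Recurrence, complication or progression of an SAE already reported: yes, without a time limit (9.2.2).
- SAEs that occurred before the decision but come to light later: yes, because 9.2.2 goes by when the event occurred.
- AEs already detected: followed until resolved or judged permanent (9.1).
- New SAEs judged unrelated: no.

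Only the last category is lost.

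**Step 5: is there an overriding rule?** None appears in 7.2, 7.4, 7.5, 9.1 or 9.2. No section makes an exception for a stop on safety grounds or sets a minimum period after the last dose.

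**The case against.** The strongest reply is that study completion is not used consistently. Protocol 3.1 gives each patient a study completion evaluation on Day 253 and asks for the end-of-study assessments in patients who discontinue the study; the assessment schedule has a study completion row at the final visit. If 9.2.2 meant the patient's own final visit, its window would reach the post-termination visit. That reading is possible, but 7.2 gives the only formal definition and it is study-level. The ambiguity is itself a reason to reconcile the sections. Even on the patient-level reading, all-cause reporting would end at an early closing visit and not at the planned Day 253.

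A second reply is that 9.2.2 governs expedited reporting to the sponsor, whereas collection is separate: 9.2.1 has all AEs captured on the CRF, and 7.5 still requires a visit. Events found at that visit may well be recorded. This softens the gap up to the visit, but no section says that collection continues after it.

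A third reply is that infection and thrombosis are named as potential risks in 3.6.2, so an investigator would often suspect causality, and 9.1 tells patients to report possibly related events after the observation period. This stands and narrows the practical loss, but it leaves causality judgement as the only filter.

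Two stronger inferences are tempting and should be resisted. A reader might conclude that the sponsor would lose the data on the events that triggered the stop. The documents do not support this: those events precede the decision, and their later course stays reportable. A reader might also conclude that meeting a 7.4 rule closes reporting automatically. It does not: 7.4 provides for review and for a hold as well as termination, and neither a hold nor an end to enrolment is a termination decision. Nor is truncation of the 36-week safety objective a contradiction in itself, since any early end cuts that objective short.

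**Conclusion.** The point holds in a limited form. As written, 7.2 and 9.2.2 together stop the reporting of new SAEs judged unrelated on the date of an early termination decision, for patients dosed as recently as that day and before the visit in 7.5. Other SAE reporting continues, so this is a gap in safety reporting and not a general loss of it.

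For a patient dosed on the decision day, the size runs from 168 days (Day 85) to 252 days (Day 1). It rests on three assumptions: the formal definition in 7.2 governs 9.2.2; the comparison is with the patient's own Day 253, leaving out the optional extension to Day 365 in 3.3; and the study is actually terminated. The overlap with full receptor occupancy, up to 70 days, also assumes that the rheumatoid arthritis figure applies here. How many patients would be affected depends on when the decision falls; enrolment is planned at about 15.

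The gap is conditional on an early stop, but it falls where all-cause data on exposed patients would be most useful, and it is cheap to close. It should be corrected.

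**What to change.** Leave the study-completion window in 9.2.2 as it is for normal conduct. Add matching text to 7.2, 7.5 and 9.2.2: for patients already dosed, an early termination decision does not end all-cause SAE reporting. As a minimum, it continues through the post-termination visit and to the end of each patient's already planned follow-up, unless the patient withdraws consent. In the same amendment, separate the two uses of study completion, for instance by keeping that term for the study and using end-of-study visit for the patient.

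The new text should be a floor that applies only on early termination. Replacing the window for everyone with 24 weeks from each patient's last dose looks simpler but would shorten present coverage: a patient who stopped after Day 1 would leave all-cause reporting at Day 1 + 168 = Day 169, one who stopped after Day 15 at Day 183, and patients in extended follow-up under 3.3 would also be cut off early.

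The cost is amendment wording, continued SAE contacts with dosed patients after an early stop, and later database closure in that case. Nothing changes if the study runs to its planned end.

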7.2.1 Lost to follow-up

For patients whose status is unclear because they fail to appear for study visits without stating an intention to discontinue or withdraw, the investigator should show "due diligence" by documenting in the source documents actions taken to contact the patient (e.g. dates of telephone calls, registered letters, etc). A patient should not be formally considered lost to follow-up until his/her scheduled end of study visit would have occurred.

7.3 Withdrawal of consent

Patients may voluntarily withdraw consent to participate in the study for any reason at any time.

Withdrawal of consent occurs only when a patient does not want to participate in the study anymore **and** does not want any further visits or assessments **and** does not want any further study related contact **and** does not allow analysis of already obtained biologic material.

If a patient withdraws consent, the investigator must make every effort to determine the primary reason for this decision and record this information. Study treatment must be discontinued and no further assessments conducted. All biological material that has not been analyzed at the time of withdrawal must not be used. Further attempts to contact the patient are not allowed unless safety findings require communicating or follow-up.

7.4 Study stopping rules

Following a review of the adverse event(s), a decision to permanently discontinue enrollment will be made jointly by the Investigator and Sponsor. The following stopping rules, based on potential preclinical findings, will serve as the basis for placing the study on hold or terminating the study.

- Two (2) or more patients experience study-drug related SAEs
- Three (3) or more treatment-related AE, CTCAE Grade 3 or higher.
- Two (2) or more patients experience CTCAE Grade 3 or higher leukopenia (WBC <1.0 x 10⁹/L)
- Two (2) or more patients experience CTCAE Grade 3 or higher thrombocytopenia (platelets <25 x 10⁹/L)
- One (1) patient experiences cytokine release syndrome
- One (1) patient has a treatment-related thromboembolic event of CTCAE Grade 3 or higher
- Two (2) or more patients experience:
 - Emergent hypogammaglobinemia defined as $\geq 50\%$ reduction in total serum IgG or IgM concentration from baseline
 - Severe systemic infection or opportunistic infection that requires treatment, e.g., sepsis, mycosis, pneumonia.
- The principal investigator or the Sponsor considers that the number and/or severity of AEs justify discontinuation of the study.
- The sponsor unilaterally requests it.

7.5 Early study termination

The study can be terminated at any time for any reason by Novartis. Should this be necessary, patients should be seen as soon as possible and treated as a prematurely withdrawn patient. The investigator may be informed of additional procedures to be followed in order to ensure that adequate consideration is given to the protection of the patient's interests. The investigator will be responsible for informing IRBs/IECs of the early termination of the trial.

8 Procedures and assessments

Table 8-1 Assessment schedule

Patients should be seen for all visits on the designated day, with the assessments performed as per schedule, within the allowed “visit/assessment window” specified in the Site Operations Manual.

Study Phase	Screening	Baseline	Treatment								Follow-up				EOS visit		
			V101		V102		V103		V104		V199		V201	V202	V203	V204	
Visit Numbers ¹	V1	V99 ¹²														V299	
Study Day(s)	Up to -28	-1	1		15		29		57		85		113	141	169	211	253
Time (post-dose)	-	-	0h ⁹	1h ⁹	-	-	-	-	-								
Informed consent	X																
Inclusion / Exclusion criteria	X	X ²															
Medical history/current medical conditions	X																
Demography	X																
Hepatitis and HIV Screen	X																
TB Test ¹⁰	X																
EBV Screen	X																
Alcohol Test and Drug Screen	X																
Blood Pressure and Pulse Rate	X	X	X	X	X	X	X	X	X	X	X	X	X	X	X	X	X
Physical examination	X		X		X		X			X		X			X	X	X
Body temperature	X	X	X		X		X		X		X		X	X	X	X	X
Body height	X																
Body weight	X	X ¹³					X		X		X		X		X		X
ECG evaluation	X	X	X		X		X		X		X		X	X	X	X	X
Pregnancy test	X	X ¹³			X		X		X		X		X		X		X
Dose administration			X		X		X		X		X						
Blood chemistry ⁴	X	X	X				X				X		X		X		X

Study Phase	Screening	Baseline	Treatment								Follow-up				EOS visit		
Visit Numbers ¹	V1	V99 ¹²	V101		V102		V103		V104		V199		V201	V202	V203	V204	V299
Study Day(s)	Up to -28	-1	1		15		29		57		85		113	141	169	211	253
Time (post-dose)	-	-	0h ⁹	1h ⁹	-	-	-	-	-								
Corporate Confidential	X	X	X				X				X		X		X		X
Hematology	X	X	X		X		X		X		X		X		X		X
Urinalysis	X	X	X				X				X		X		X		X
Cytokine assessment			X	X	X	X	X	X	X	X	X	X					
Coagulation Panel		X ¹³		X		X		X		X		X	X	X		X	X
Concomitant therapies													as required				
Serious adverse events													as required				
Adverse events													as required				
Immunogenicity ³			X						X				X	X	X		X
Comments													as required				
Study completion information																	X
TSH	X	X	X		X		X		X		X		X	X	X	X	X
Total and free T3 & T4	X	X	X		X		X		X		X		X	X	X	X	X
PK (CFZ533) ⁹			X	X	X	X	X	X	X	X	X	X	X	X	X		X
Free & total CD40 on B cells ⁵				X			X		X		X		X	X	X		X
Soluble CD40 ⁵				X			X		X		X		X	X	X		X
Soluble CD154 ⁵				X			X		X		X		X	X	X		X
Exploratory Biomarkers in Serum ⁶		X	X		X		X		X		X		X	X	X	X	X
Corporate Confidential	X	X	X		X		X		X		X		X	X	X	X	X
Corporate Co	X	X	X		X		X		X		X		X	X	X	X	X
Corporate Confidential Information			X ⁸														
Corporate Confidential Information		X ¹³									X						

¹ Visit structure given for internal programming purpose only

² Only those inclusion/exclusion criteria that are specific for baseline visit

³ Immunogenicity: 0-hour sample is taken **pre-dose**

⁴ Corporate Confidential Information

⁵ On days when patient is dosed, sample is taken **pre-dose** (0-hour)

⁶ Corporate Confidential Information

⁷ Corporate Confidential

Information

Corporate Confidential Information

⁹ 0-hour sample (or assessment) is taken **pre-dose**, 1-hour sample is taken 1 hour **AFTER** the END of infusion

¹⁰PPD or QuantiFERON TB-gold test

Corporate Confidential Information

¹²The baseline visit assessments can be completed on Day 1 (pre-dose) when the first dose (Day 1) is received within 7 days of the screening visit.

¹³These assessments will be completed prior to the study treatment on Day 1 (Visit 101, **pre-dose**) if Day 1 is scheduled within 7 days of the screening visit (Visit 1).

